Title: Evaluation of pain alleviating strategies during allergy shots (Subcutaneous immunotherapy): A randomized controlled study (Pain Perception with Allergy Shot Techniques: PPAST)

Principal Investigator

- [name] MSN, APRN, PCNS-BC, CPEN

Co-Investigators

- [name] [name], CPN
- [name] [name], AE-C
- [name] [name], CPN
- [name] [name]
- [name] [name], CPN
- [name] [name], CPN
- [name] [name], CPN
- [name] [name]
- [name] MD
-

Research Coordinators

- [name], BSH
- [name], BSN, RN, CCRC
- [name], BSN, RN, CCRC

Project Consultant / Data Analyst

- [name] MSN, ARNP, PCNS-BC, FNP-BC

Rationale and Purpose

Subcutaneous Immunotherapy (allergy injections) is a potentially disease-modifying therapy that is effective for the treatment of allergic rhinitis/conjunctivitis, allergic asthma and stinging insect hypersensitivity. Pain, which results from the irritation of nearby nerves is a common concern of patients, particularly in children, during or after the injections. This can be a stressful and negative experience for the children. There are various techniques available to minimize pain in general. However, there is a lack of published research on how to use these techniques in children receiving allergy injections. The purpose of this study is to evaluate and compare the efficacy of the standard of care method (Ethyl Chloride/Pain Ease Spray) and three non-pharmacological pain control devices (Buzzy Bee I, Buzzy Bee II and Shot Blocker) in decreasing the perception of pain during subcutaneous allergy injection in a pediatric allergy/immunology clinic setting.

Objective

- Evaluate and compare the effectiveness of utilizing various techniques to reduce the perception of pain during subcutaneous allergy injections in children

Possible Risks and Benefits

Risk Assessment

- The risks associated with study participation are consistent with standard of care risks. Potential risk for the study participants may be possible allergic reaction/skin irritation from the cold spray or ice pack or an increased level of anxiety.

Benefits Assessment

- The potential benefit associated with this research study includes a better understanding of study participant's response to their assigned distraction technique. This study may help identify which technique is more beneficial to use in children receiving subcutaneous immunotherapy to decrease the perception of pain and reduce anxiety related to immunotherapy treatment.

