The four study groups are:

- Interventional Groups
 1. Shot Blocker®
 2. Buzzy I (*with ice pack-wings*)
 3. Buzzy II (*without ice pack-wings*)
- Control Group
 4. Ethyl Chloride/Pain Ease Spray

Before applying the assigned distraction method:

- Prior to randomization, the investigator will interview the parent to obtain the information needed to complete the Parent Demographic-Health-Treatment Questionnaire (Attachment V). The investigator will review the responses for any indicator of study ineligibility, ie, analgesic medication window.
- The investigator or study staff will review the Wong-Baker FACES Pain Rating Scale with the child. The child will be given a Wong-Baker FACES Pain Rating Scale form and asked to circle the face which most closely matches their current level of pain awareness prior to any intervention. (Attachment IV-a)
- The investigator or study staff will review the Numeric Pain Rating Scale (Attachment IV-b) with the parent. The parent will be instructed to circle the number on the scale which most closely matches their perception of their child's pain level immediately after receiving the allergy injection.

Application of the distraction method and administration of the allergy injection:

- The investigator will apply the assigned distraction method per method specifications to the injection site area (subcutaneous region of the back of the upper arm).
- The investigator will administer the subcutaneous allergy injection(s) within the time frame specified for the assigned distraction device utilized or per the standard of care guidelines for the Pain Ease Spray, as appropriate. If the child's treatment plan includes more than one injection, the assigned group technique will be utilized for all injections at the visit.

Post allergy injection procedures:

- Immediately following the allergy injection, the child will be provided with a second Wong-Baker FACES Pain Rating Scale form and be asked to circle the face which most closely matches their post-injection level of pain awareness.
- Immediately following the allergy injection, the parent will be reminded to circle the number on the Numeric Pain Rating Scale which most closely matches their perception of the child's post-injection pain level.
- The participant and parent will then complete the routine 30 minute wait time for post allergy injections.

Study participation is complete at the end of Visit 2.

Prohibited Medications

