Analgesic medications administered within eight hours of Visit 2 are prohibited.

Adverse Event (AE)

An AE is any unfavorable and unintended sign, symptom temporally associated with the use of the study technique and does not imply judgment about causality.

AE's associated with the randomized intervention will be collected at Visit 2. The AE's relationship to the distraction technique will be assessed using the following guidelines for causality and grading severity. AE's related to the allergy injection will not be captured in this study.

AE Relationship to Study Distraction Technique Guide

Relationship to Study Distraction Technique	Comment
Definitely	An event that follows a reasonable temporal sequence from administration of the study distraction technique; that follows a known or expected response pattern to the suspected study distraction technique; that is confirmed by stopping the use of the study distraction technique; and this is not explained by any other reasonable hypothesis.
Probably	An event that follows a reasonable temporal sequence from administration of the study distraction technique; that follows a known or expected response pattern to the suspected study technique; that is confirmed by stopping the use of the study distraction technique; and that is unlikely to be explained by the known characteristics of the subject's clinical state or by other interventions.
Possibly	An event that follows a reasonable temporal sequence from administration of the study distraction technique; that follows a known or expected response pattern to that suspected study distraction technique; but that could readily have been produced by a number of other factors.
Unrelated	An event that can be determined with certainty to have no relationship to the study distraction technique.

AE Severity Grading

Severity (Toxicity Grade)	Description
Mild (1)	Mild; asymptomatic or mild symptoms; clinical or diagnostic observations only; intervention not indicated
Moderate (2)	Moderate; minimal, local or noninvasive intervention indicated; limiting age-appropriate Instrumental activities of daily living (e.g., preparing meals, using the telephone, managing money)
Severe (3)	Severe or medically significant but not immediately life threatening; hospitalization or prolongation of hospitalization indicated; disabling; limiting self-care activities of daily living (e.g., bathing, dressing, feeding self, using toilet, taking medications)

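### Leaving injection-related adverse events unrecorded conflicts with the plan's own AE definition and can bias any by-arm AE summary

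*Combined protocol and SAP*

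**What the plan says.** The Adverse Event (AE) section makes three statements that bear on capture.

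- The definition covers any unfavourable, unintended sign or symptom that is "temporally associated with the use of the study technique and does not imply judgment about causality".
- Collection is then narrowed: "AE's associated with the randomized intervention will be collected at Visit 2".
- One class of event is removed: "AE's related to the allergy injection will not be captured in this study".

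The relationship table that follows has four categories. Definitely, Probably and Possibly each require that the event fit a response pattern known for or expected of the technique. Possibly also allows that other factors could easily explain the event. Unrelated requires certainty that the technique played no part.

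Elsewhere, under Visit 2, the investigator is to "apply the assigned distraction method per method specifications to the injection site area" and then gives the injection. The Risk Assessment names "possible allergic reaction/skin irritation from the cold spray or ice pack", and also increased anxiety, which it ties to no arm. The Data Analysis section lists adverse reactions among the data to be evaluated.

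**The concern.** An AE definition that is neutral on cause works only if events are recorded first and attributed afterwards. Here one attribution, to the injection, comes first and removes the event. The relationship scale then sees only events that have already passed a causal filter, and the plan keeps no record of that filter.

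The filter need not act equally in the four arms. Whoever applies the technique knows which one it is. The protocol's own risk statement leads staff to expect skin effects from the spray and the ice wings, but not from ShotBlocker or from vibration alone. If a mark on the arm is accepted as technique-related in one arm and set aside as injection-related in another, the AE counts reflect expectation as well as what happened. The study hopes to identify which technique is more beneficial, so readers are likely to look at AE counts by arm even without a formal test.

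**Working it through.** The plan gives no AE rate, so there is no figure to reproduce. The only related count, 4 arms × 25 envelopes = 100, agrees with the stated total. The check is mainly a comparison of the text, followed by an illustration. The Buzzy arms are identified by content below, because the protocol assigns the labels I and II in opposite ways.

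**Step 1. Definition against capture rule.** The definition says that it "does not imply judgment about causality". The capture rule cannot be applied without such a judgment. An injection reaction that follows use of the technique meets the definition and could be rated on the scale, yet the rule bars it from the record.

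**Step 2. Who judges.** The AE section names no assessor. The Visit 2 procedures have the investigator apply the technique and give the injection, and no masked assessor is described. The blinded envelope in the design section concerns allocation only. That the judgment is made with knowledge of the arm is therefore an inference, though the natural one.

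**Step 3. Can site or timing separate the causes?** Not reliably. According to the attachments:

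- ShotBlocker is pressed over the site, and its placement is repeated if more than 20 seconds pass before the injection.
- The spray goes on the treatment area for 3 to 7 seconds before the needle.
- Buzzy sits on the site for 15 to 60 seconds and is then moved proximally and held there during the shot.

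Overlap differs by device, but each is in contact with the injection site close to the time of injection.

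**Step 4. Does the scale treat arms alike?** Local irritation in a spray or ice-wing child fits the risk named in the Risk Assessment, so a related category is open. The same irritation in a ShotBlocker or vibration-only child matches no skin risk that the protocol names, and Unrelated demands certainty. Non-capture as an injection reaction is then the easy route.

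**Step 5. Is the event collected elsewhere?** The Data Collection section says it targets reactions to allergy injections, but it refers to Attachment V. That form is completed before the shot and asks about past symptoms, so it cannot hold a Visit 2 reaction.

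**Step 6. Illustration only.** All rates here are assumptions. Let p be the true local reaction rate and c the probability that an event is captured rather than set aside. Recorded rate = p × c.

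| True rate (arm A, arm B) | Capture (A, B) | Recorded (A, B) | Recorded difference, B − A |
|---|---|---|---|
| 20%, 20% | 20%, 60% | 4%, 12% | 8 points |
| 10%, 10% | 20%, 60% | 2%, 6% | 4 points |
| 40%, 40% | 20%, 60% | 8%, 24% | 16 points |
| 20%, 20% | 50%, 50% | 10%, 10% | 0 |
| 10%, 30% | 50%, 50% | 5%, 15% | 10 points (true 20) |
| 10%, 30% | 80%, 20% | 8%, 6% | −2 points (true 20) |
| 10%, 30% | 100%, 100% | 10%, 30% | 20 points (true 20) |

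In the first row the counts are 25 × 0.04 = 1 and 25 × 0.12 = 3. The threefold ratio is simply the assumed capture ratio, 0.60 / 0.20 = 3. The table shows that a false difference can appear and that a true one can shrink or reverse. It does not show which will happen here. Complete capture in every arm removes the distortion.

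**The case against.** The strongest reply is that the plan already deals with ambiguous events. Possibly accepts events with other ready explanations, and Unrelated demands certainty. On a consistent reading, doubtful site events are recorded as Possibly and only clear injection reactions are left out. This has real weight and narrows the problem. It does not remove it: no rule says that an ambiguous event must be recorded rather than set aside, and Possibly itself requires a pattern known for or expected of the technique, which brings back the difference between arms.

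Second, the sole objective is pain perception. Adverse reactions are only listed as data to be evaluated, with no between-arm AE analysis. This stands. A reader might infer that the rule biases a planned safety comparison, but the documents describe none.

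Third, the numerical example contains its own answer, and one versus three events of 25 would be unremarkable by chance (Fisher p = 0.61). This also stands, and it is why the example is offered only to show the mechanism.

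Fourth, a reader might infer that uncaptured events are lost for good, or that the two causes produce identical reactions. The documents support neither. Institutional injection guidelines and an injection chart exist, but the protocol does not say what the chart records and gives the study no route to it. Nothing in the text compares how reactions from the two causes look.

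**Conclusion.** The concern holds in a limited form. The conflict between the capture rule and the AE definition is plain in the text. So is its consequence, that cause is judged before recording. That this can bias a by-arm summary of adverse reactions follows if two inferences are accepted: that the assessor knows the arm, and that the named risks influence attribution.

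It would go too far to say that the rule does bias the results, or that it inflates AEs in the cold arms by any given amount. The text suggests a tilt towards recording more in those arms, but capture probabilities and true rates are unknown. Equal capture with equal true rates would give no false difference, and incomplete capture could equally hide a true one. The child and parent pain scores are not affected. The change is worth making before enrolment, but the trial's main question does not depend on it.

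**What to change.** Delete the sentence that excludes injection-related AEs, and align the collection sentence with the timing-based definition. Record every AE observed or reported at Visit 2, from application of the technique to the end of the routine 30-minute wait, whatever the suspected cause and in the same way in all four arms. After recording, rate relationship to the technique and, as a separate item, relationship to the injection. Tabulate all AEs and technique-related AEs by arm.

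The cost is a few more AE lines, one further relationship rating, and a higher total AE count from expected injection reactions, which the table should explain. Families already stay for the wait, so no extra visit time is needed. The protocol describes no study observation during that wait, however, so staff would need one uniform way of asking about and noting events for every child, including those who receive several injections.

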Study Design and Duration

This is a randomized controlled study. Approximately 100 children, age 4 – 17 years, who are currently receiving subcutaneous immunotherapy, will randomly select a blinded envelope which assigns the distraction technique to be utilized during their study participation. There will be 25 envelopes assigned to each study group for a total of 100 envelopes. Each envelope will contain a paper with a colored sticker for the associated group assignment and number sequence.

The distribution of group assignment by number sequence and color is as follows:

- Interventional Groups
 1. Shot Blocker® # 1-25 (RED)
 2. Buzzy I (vibrating only) # 26-50 (GREEN)
 3. Buzzy II (vibrating and ice wings) # 51-75 (BLUE)
- Control Group
 4. Ethyl Chloride/Pain Ease Spray # 76-100 (YELLOW)

The three interventional groups are currently marketed distraction devices. The control group is the current clinical standard of care option for pre-allergy injection application.

The study consists of two visits. Both visits will be conducted during the participants routine clinic visit for allergy injections. At the first visit the investigator will assess eligibility. An overview of the study requirements will be provided to parent/child and consent/assent will be obtained.

During the second visit, the child will be randomized to a distraction technique or standard of care group to be utilized with the allergy injection(s) administered at this visit. Adherence with institutional allergy injection guidelines will be maintained. Prior to the application of the distraction method, the investigator will interview the parent to collect data related to demographic information and their child's current allergy health and treatment regime. The child's pain perception will be assessed before and after the allergy injection. The parent's perception of their child's pain will be assessed after the allergy injection. The investigator will provide information on the application of the randomized method and will provide instruction on the completion of the pain scales and questionnaires. The investigator and study staff will not indicate a method preference or guide the child or parent with their pain level responses. After completion of the second visit, the child's study participation is complete.

Inclusion & Exclusion Criteria

Inclusion Criteria

- Children aged 4-17 years on injection immunotherapy

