Discontinuation and Replacement of study participants

A child has the right to withdraw from study participation prior to the completion of Visit 2. Early withdrawal participants will be replaced one to one.

Participant ID assignment

The study participants will receive a Participant ID at Visit 1 which will be used for all data collection. The Participant ID used will range from 001 to 100. If a study participant withdraws before the completion of Visit 2, the Participant and associated group assignment will be replaced. Replacement Participant ID's will be sequential beginning with the number 101.

Data Collection

Medication administration data collected will be limited to the participant's current immunotherapy vial and dosing, distraction method utilized, site of the application method and, if applicable, antihistamine use and pain medication use. Demographic data collected will be age, race and gender. Symptom and health data point collection will target allergy injection reactions and the presence of allergic rhinitis, asthma and atopic dermatitis. (Refer to Attachment V). Pain perception data will be collected from both the child and parent using facial and numeric pain scales (Refer to Attachment IV).

All data collected will be entered into an EXCEL data collection tool and stored on password protected, secure computers. The data will accessible only to the investigators and research coordinators in the study.

Data Analysis

Quantitative component data collected and evaluated for this study will include the number of patient participants within the allergy department, randomized interventions used, diagnoses including allergic rhinitis, asthma and atopic dermatitis, immunotherapy medication and dose, antihistamine and pain medication utilization, patient and parental pain scores, adverse reactions, age, race, and gender.

Quantitative component data collected for this study will be extracted into Microsoft Excel spreadsheets and analyzed using Excel functions. Target population demographic characteristics will be analyzed using descriptive statistics by the principal investigator with the level of significance set at <0.05.

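### The only objective, a four-arm comparison of perceived pain, has no prespecified rater, outcome, test, contrasts or multiplicity rule

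*Combined protocol and SAP*

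**What the plan says.** The Objective section has one entry: "Evaluate and compare the effectiveness of utilizing various techniques to reduce the perception of pain during subcutaneous allergy injections in children". The Benefits Assessment says what the result is for: "This study may help identify which technique is more beneficial to use in children receiving subcutaneous immunotherapy".

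Under Study Design and Duration there are four arms of 25 envelopes: three devices labelled interventional, and the cold spray labelled control. The same section says "The child's pain perception will be assessed before and after the allergy injection". The parent rates the child's pain after the injection only. Study Procedures, Visit 2, gives the instruments. Before the technique is applied, the child is "asked to circle the face which most closely matches their current level of pain awareness prior to any intervention"; afterwards the child is "asked to circle the face which most closely matches their post-injection level of pain awareness". The parent uses a 0-10 numeric scale.

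The Data Analysis section lists pain scores from both raters among the data to be evaluated, and says that the data go into Excel and are analysed there. The only sentence with a significance level is "Target population demographic characteristics will be analyzed using descriptive statistics by the principal investigator with the level of significance set at <0.05".

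On the arms, Study Design and Duration has "Buzzy I (vibrating only) # 26-50 (GREEN") and gives Buzzy II the ice wings. The Visit 2 list of groups has "Buzzy I (*with ice pack-wings") and gives Buzzy II none; the heading of Attachment II agrees with the Visit 2 list.

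**The concern.** The outcome domain, scales and timing are given. The step from scores to a conclusion is not. Five choices are open:

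- **Rater:** child FACES score or parent numeric score.
- **Child outcome:** post-injection score or change. This is open for the child only, because the parent gives no pre-injection rating.
- **Test:** no between-arm test or model is named.
- **Contrasts:** three device-versus-spray comparisons or all six pairs.
- **Multiplicity:** no rule.

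Each could be settled after the scores are seen. A statement that one technique is more beneficial could then come from whichever comparison turned out favourable, and the plan gives no way to state its false-positive risk.

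A separate problem affects what a contrast means. The numbered, coloured envelopes identify the arms, so a Buzzy contrast can be computed. With opposite definitions in the text, however, the reader cannot tell which technique it evaluates.

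**Working it through.** **The plan's own figure.** 4 arms × 25 = 100, which agrees with the stated total of about 100. No power, effect size, SD, sidedness or test is given, so the sample size cannot be reproduced beyond that product.

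**Candidate analyses.** Three outcomes are open (child post, child change, parent post), with 3 or 6 contrasts each: from 3 tests (one outcome, device versus spray) to 3 × 6 = 18 (every outcome, every pair).

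**False-positive risk if 0.05 were used unadjusted.** From the protocol: 25 per arm and four arms. Assumed: two-sided 0.05 applied to pain, two-sample t-tests (48 df) and no true difference. If tests were independent, the risk would be 1 − 0.95^3 = 14.3% for three and 1 − 0.95^6 = 26.5% for six. The tests share arms, so these are too high. Simulation with normal scores (200,000 runs per setting; 40,000 for the last row) gives:

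| Outcomes tested | 3 contrasts | 6 pairs |
|---|---|---|
| One rater | 12.5% | 20% |
| Two raters, child-parent correlation 0.9 to 0.3 | 17-23% | 27-36% |
| Two raters plus child change, equal pre and post SD, pre-post correlation 0 to 0.6 | 24-32% | 37-47% |
| As above, but pre-score SD a quarter of post SD, pre-post correlation 0.3 | not tabulated | about 30-39% |

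The last row matters because pre-injection scores may cluster near 0. If every pre-score were 0, change would equal the post score and add nothing. A single omnibus test, or Tukey on all six pairs of one endpoint, holds 5%.

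**Price of control with 25 per arm.** The SE of a difference is SD × √(2/25) = 0.283 SD. Critical t values on 96 df are 1.985 (unadjusted), 2.387 (Dunnett, three contrasts) and 2.615 (Tukey, six pairs). The detectable difference at 80% power is approximately (critical t + 0.842) × 0.283 SD; the noncentral t gives the exact values below. Power is for a 2-point difference (one FACES step), at assumed SDs.

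| | Detectable at 80% | Power, SD 2 | SD 2.5 | SD 3 |
|---|---|---|---|---|
| Unadjusted | 0.80 SD | 94% | 80% | 65% |
| Dunnett | 0.915 SD | 87% | 67% | 49% |
| Tukey | 0.98 SD | 82% | 59% | 40% |

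These figures take no gain from a baseline covariate. With a pre-post correlation of 0.3, the Tukey figure becomes 0.98 × √(1 − 0.09) = 0.935 SD.

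**Why the covariate settles post versus change.** In the linear model post = arm + b × pre, subtracting pre from both sides gives change = arm + (b − 1) × pre. The arm terms are unchanged, so both outcomes give identical contrasts.

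**The case against.** The strongest reply is that the authors probably meant 0.05 to cover the pain comparison, that scales and timing are clear, and that a small, low-risk study which says only that it may help identify a technique makes no confirmatory claim. Part of this stands. The text makes no power claim, and labelling the comparison exploratory would be an honest alternative. But extending 0.05 to pain leaves all five choices open, and the gap concerns the study's only objective.

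A reader might infer more than the documents support:

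- *That the plan runs unadjusted tests with a false-positive rate of up to 47%.* It does not say so. The 0.05 is attached to demographics, and the percentages depend on assumed tests, correlations and SDs. The top of the range shrinks to about 39% if pre-scores vary little.
- *That six pairwise contrasts are required.* The objective of comparing techniques fits six pairs; the control label on the spray fits three device-versus-control contrasts. The documents do not settle it.
- *That the Buzzy contradiction undermines every comparison.* ShotBlocker versus spray is unaffected.

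**Conclusion.** The gap is real and should be closed before any data by arm are examined. As written, no result on the sole objective could be called prespecified, and the one significance level sits on a description that involves no test. This rests on the text alone: the Data Analysis section reads as complete, and neither redaction nor missing figures explain the omission.

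The size is illustrative, not a bound. The 12.5% to 36% range for one or two raters assumes unadjusted two-sided t-tests, 25 per arm, no true difference and a child-parent correlation of 0.3 to 0.9. What adding child change contributes depends heavily on how much pre-injection scores vary. The contradictory Buzzy definitions are a separate defect, limited to contrasts involving those two arms.

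**What to change.** Before data by arm are seen:

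1. Reconcile the Buzzy I and II definitions across Study Design and Duration, the Visit 2 group list and Attachment II.
2. Name the child's post-injection FACES score as the primary endpoint, since the objective is pain perception in children and only the child is rated before and after. State which rating counts when a child has more than one injection, which Visit 2 allows. Make the parent score secondary.
3. Use one four-arm linear model of that score with the pre-injection FACES score as covariate, and report no separate change-score results. Give the model without the covariate as a sensitivity analysis, because Visit 2 puts the pre-injection rating before the intervention but not clearly before the envelope draw.
4. State one contrast family, controlled at familywise 0.05: three device-versus-control contrasts (Dunnett) or all six pairs (Tukey). The sponsor chooses and justifies one in advance. Give parent results as estimates with confidence intervals only.
5. Describe demographics by arm without p-values.

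If data by arm have already been seen, label the comparison exploratory or post hoc.

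The cost is SAP wording, software beyond basic Excel functions for the adjusted model and contrasts, and the power loss tabulated above: at SD 2.5, from 80% to 67% (Dunnett) or 59% (Tukey) for a 2-point difference, before any covariate gain.
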